### **6.3 IM Group**

HIV-infected subjects in the IM Group will receive the first two doses of study drug in accordance with the Trogarzo® prescribing information (diluted in normal saline and administered over 15 minutes via IVI) at Day 1/Baseline and again at Day 15. The next four doses of Trogarzo® will be administered as an IM injection. At Day 85 (12 weeks), IM Group HIV-infected subjects will revert to diluted IVI dosing over 15 minutes in accordance with the Trogarzo® prescribing information.

HIV-uninfected individuals will receive four doses of Trogarzo® (pre-Steady State Phase) as described above for Core Group HIV-uninfected individuals prior to the Study Treatment Phase. In the Study Treatment Phase, HIV-uninfected subjects will receive the first two doses of Trogarzo® in accordance with the prescribing information (diluted in 250 mL normal saline and administered over 15 minutes via IVI) at Day 1/Baseline and again at Day 15. The next four doses of Trogarzo® will be administered as an IM injection.

HIV-uninfected subjects will discontinue dosing after the Day 71 study drug administration. The scheduled visit at Day 113 (16 weeks) for the HIV-uninfected IM Group subjects is for safety follow-up only, and this visit may be conducted by telephone if no clinic visit is needed for this purpose. Trogarzo® administration at Day 99/follow-up should be conducted in the routine manner as employed prior to the study, through the primary care provider. The Day 99 EOS visit in the

HIV-uninfected IM group subjects that is 28 days after the last dose of Trogarzo® must be completed in the clinic.

Safety assessments, including collection of blood and urine specimens for safety laboratory testing, as well as HIV-1 viral load and archive and viral resistance samples (HIV-infected individuals only), will be conducted every 2 weeks beginning at Day 1/Baseline and continuing through Day 85 [12 weeks]) for HIV-infected subjects, and through Day 99 for HIV-uninfected healthy volunteers. In addition, subjects will also have non-laboratory safety assessments (vital signs, recording of concomitant medications, assessment of IM injection site) conducted during visits on intervening weeks between the study IM drug administrations through the EOS. AEs are collected at all timepoints from time of consent.

Targeted physical examinations will be conducted at various visits from Day 1 through Day 85 (12 weeks) for HIV-infected subjects, and through Day 99 for HIV-uninfected healthy volunteers. Weight will be recorded at Screening and again at EOS. Immunogenicity samples will be collected at Day 1/Baseline and again at EOS (Day 85 [12 weeks] for HIV-infected subjects or Day 99 [14 weeks] for HIV-uninfected healthy volunteers). IM Group subjects will be asked to return for the final study assessments indicated for the EOS and Follow-up visits (Day 99 [14 weeks] for HIV-infected and Day 113 [16 weeks] for HIV-uninfected see Table 4). Subjects who are discontinued or who withdraw from the study prematurely are also requested to complete the assessments for these two study visits, unless they are re-enrolled HIV-infected individuals participating in the IM study.

Pharmacokinetic samples will be collected after study drug doses at Day 1/Baseline and Days 15, 57, and 71 at the following timepoints: 48 hours, and 7, 10, and 14 days after study drug administration). This schedule will require additional visits solely for sample collection on Study Days 3, 8, 11, 17, 22, 25, 59, 64, 67, 73, 78, and 81. For IM dosing, the 2- and 14-day post-dose serum concentration data are required for the estimation of PK AUC.

Discontinued HIV-1 infected participants who re-enroll after receiving a loading dose of 2000mg IVI and at least one maintenance dose of 800mg IVI given according to the label prior to Day 1 enrollment will not undergo PK assessments between Baseline and the Day 29 visits since these PK samples will already have been collected during the subject's initial study participation. The PK assessments of the re-enrolled participants will be compared between the IVI from their first enrollment and IM from their second enrollment.

In HIV-1 uninfected subjects PK samples will also be drawn on Days -55, -41, -27, and -13.

Study participants who:

1. miss 2 consecutive visits or
2. have more than one treatment visit out of window or
3. have 3 non-treatment visits over 4 weeks that are out of window

will be discontinued from the study and may be replaced. For this reason, it is important to enroll only participants who in the judgement of the investigator are likely to be compliant with the study visit and sample collection schedule. However, discontinued HIV-1 subjects in the IM portion of the study may rescreen and re-enroll in the event of the need for a loading dose with 2000mg IVI of Trogarzo® followed by at least one maintenance dose of 800 mg IVI and with agreement to adhere to the subsequent study schedule.

Refer to Table 4 for details on procedures for each scheduled study visit and for PK sampling timepoints.

## **6.4 Follow-up Visits: Day 113 (Sentinel Group and HIV-Uninfected IM Group) / Day 99 (Core and HIV-infected IM Groups)**

All subjects are to have a Follow-up Visit - at Day 113 (16 weeks) for the Sentinel and HIV-uninfected IM Groups, and at Day 99 (14 weeks) for the Core and HIV-infected IM Groups for collection of safety information. The medications taken during the follow-up period (the period from the previous scheduled study visit – Day 99 [14 weeks] for the Sentinel and HIV-uninfected IM Groups, Day 85 [12 weeks] for the Core and HIV-infected IM Groups through to this Follow-Up Visit) should be captured as concomitant medications in the EDC system. Any changes to background ARV medications should also be recorded, along with a reason for the change. AEs will be collected at this visit. If it is not necessary for the subject to present at the clinic for these procedures, this visit may be conducted via telephone. Administration of Trogarzo® for this visit should be conducted in the routine manner as employed prior to the study, through the primary care provider.

Subjects that withdraw or are discontinued from either study group should be followed for 28 days after receiving administration of study drug either by IV infusion, bolus, push, or IM, except for discontinued HIV-infected IM subjects that are re-enrolling into the study.

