#### STUDY DRUG ADMINISTRATION AND AFTER

Administer study drug via IVI – study drug diluted in 250 mL normal saline and administered IV over 15 minutes per Trogarzo® prescribing information

Administer study drug via IM injection

Observe subject for 15 minutes if HIV infected and 60 minutes if HIV uninfected after administration; record vital sign measurements after dose administration and again at end of observation period

\* Screening visit to be conducted for HIV-infected patients ONLY. See [Table 2](#) for Screening and Pre-Steady State Phase Schedule of Events

 All prior ART will be recorded at Screening; subsequent visits will only record changes to ART.

 Abbreviated physical examination includes examination of lymph nodes, respiratory and cardiovascular systems, abdomen, extremities, and nervous system.

 Only record AEs that are related to study procedures before administration of the first dose; after administration of first dose, assessments will include evaluation of injection site for reaction.

 Subjects need not fast before blood sampling.

 Serum FSH test to be conducted on postmenopausal females at Screening only.

 Pre-dose samples to be collected within 1 hour before the start of the infusion.

 At Baseline and at Day 15, subjects in the IM Group will receive study drug diluted into 250 mL normal saline as an 800 mg IV infusion over 15 minutes, per Trogarzo® prescribing information. At Day 29 IM Group subjects will begin receiving study drug as 800 mg undiluted Trogarzo® administered by IM injection once every 2 weeks.

 Any abnormalities observed need to be recorded on the AE case report form.

 HIV-infected IM group subjects only.

 HIV-uninfected IM subjects only.

 Day 85 is end of study for HIV-infected subjects.

 Day 99 is follow-up for HIV-infected subjects and is end of study for HIV-uninfected subjects.

 PK visits between Baseline and Day 29 will not be required for HIV-infected subjects participating in the IM portion of TMB-302 who have re-enrolled after receiving a 2000mg loading dose and one 800 mg dose of Trogarzo® by IVI prior to study re-enrollment since these PK samples will already have been collected during initial study participation.

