or are discontinued from the study prematurely will undergo all safety assessments and follow-up procedures as described for Day 99 (14 weeks) and Day 113 (16 weeks) for the Sentinel and HIV-infected IM Groups, and for Day 85 (12 weeks) and Day 99 (14 weeks) for the HIV-1 infected Core Group and the HIV-uninfected IM Group, respectively, and Day 99 for the HIV-uninfected Core Group subjects, with the exception of re-enrolled HIV-infected subjects participating in the IM study. Subjects who fail to return for final assessments will be contacted by the site personnel in an attempt to have the subjects comply with the protocol. A minimum of two documented phone calls should be made over the course of at least 2 weeks. If the site personnel receive no response, they should send a certified letter requesting that the subject contact the site regarding his or her status in the study. If the subject does not respond at this point, the date the certified letter was mailed will be considered the date of study withdrawal.

In the event of a subject death during the study, the date of death (as listed on the death certificate) will be used for the date of study discontinuation.

It is vital to obtain follow-up data on any subject withdrawn because of an AE or SAE. In such cases, the subject will be followed to satisfactory resolution or until the investigator deems the event to be chronic or the subject to be stable. In any case, every effort must be made to undertake protocol-specified safety follow-up procedures.

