## 6.5 Early Withdrawal Procedures

Subjects who withdraw or are discontinued from the study at any time before EOS (Day 85 (12 weeks) for HIV-infected Core or IM Groups, or Day 99 for Sentinel and HIV-uninfected Core or IM Groups) will be asked to complete all EOS procedures to ensure safety and to collect as much study data as possible, except for discontinued HIV-infected IM subjects that are re-enrolling into the study. These individuals should be followed for 28 days after receiving study drug administration.

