### **8.3 Reporting Adverse Events**

The investigator is responsible for reporting to the Sponsor or designee all AEs that are observed or reported by the subject during the study (from the time the subject signs informed consent until 28 days after the last dose of the administration of study drug is given whether by IV infusion, bolus, or push or IM injection), regardless of their relationship to study drug or its experimental administration or their clinical significance. Subjects will be instructed to contact study site personnel at any time after informed consent if any symptoms develop. AEs will be documented in the subject's source documents and recorded in the AE section of the EDC system.

To ensure compliance with FDA regulations (21 Code of Federal Regulations [CFR] 312.64), site investigators must report immediately all AEs that meet the SAE criteria, regardless of presumed relationship to the study drug or its experimental administration, to the Sponsor. The Sponsor will carefully review the SAE information to monitor the study drug's toxicity profile and subject safety. If any event meets the FDA's reporting criteria, it will be submitted to the FDA as an IND Safety Report (21 CFR 312.32).

All AEs reported or observed during the study must be recorded in detail in the AE section of the EDC system and followed to a satisfactory resolution or until the investigator deems the event to be chronic or the subject to be stable.

Information to be collected includes the event term, date of onset, date of resolution, investigator-specified assessment of severity and relationship to study drug or its experimental administration, and seriousness, as well as any required treatment or evaluations and outcome.

Pre-existing conditions (present before the start of the AE collection period) are considered concurrent medical conditions and should NOT be recorded as AEs. However, if the pre-existing condition worsens in severity, the investigator must report it as an AE.

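### HIV-infected IM subjects who re-enroll are waived from follow-up that Protocol Sections 8.3 and 3.1 require without exception, and no antibody sample is scheduled after their first IM course until the new Day 1

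*Protocol*

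**What the plan says.** **The waiver.** Section 6.4 wants anyone who withdraws or is discontinued to have 28 days of follow-up after dosing by any route, "except for discontinued HIV-infected IM subjects that are re-enrolling into the study". Section 6.5 asks early withdrawals "to complete all EOS procedures to ensure safety and to collect as much study data as possible, except for discontinued HIV-infected IM subjects" who are re-enrolling. Sections 5.3.2 and 6.3 carry the same exception for final assessments, but word it for subjects who have re-enrolled. Section 6.5 closes with "These individuals should be followed for 28 days after receiving study drug administration".

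**The general rule.** Section 8.3 makes all AEs reportable "from the time the subject signs informed consent until 28 days after the last dose of the administration of study drug is given", IM injection included. Section 3.1 (All Groups) sets 28 days of monitoring after the last administration. Section 6.3 collects AEs in the IM Group at all timepoints from consent. None of these makes an exception for re-enrollers.

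**Re-enrollment.** A Discontinuation Visit and a Screening Visit must be completed first (5.3.2). The loading dose is given at least 4 weeks before the new Day 1, and its day may double as the Discontinuation or Screening Visit (3.1). Table 4 footnote 3 reads "Only record AEs that are related to study procedures before administration of the first dose".

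**Subjects who stop and do not re-enroll.** Section 5.3.2 sends them to assessments "as described for Day 99 (14 weeks) and Day 113 (16 weeks) for the Sentinel and HIV-infected IM Groups". Section 6.5 and Table 4 footnote 11 make Day 85 the EOS visit for HIV-infected IM subjects.

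**Analysis.** Item 2b of the IM SAP addendum presents only second-enrollment data for everything other than PK.

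**The concern.** IM safety is a primary objective; viral load and immunogenicity are secondary. A subject whose IM dosing was interrupted has still been exposed to IM drug, and the plan should state plainly what is collected after that exposure. Instead, one section waives follow-up that two others require, a further sentence can be read either way, and the one visit that could fill the gap has no content. Two sites could follow the protocol in good faith and collect different safety data. The end-of-IM antibody sample, the only scheduled look at immunogenicity after IM dosing, is not asked of these subjects at the end of their first IM course.

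**Working it through.** The plan states no figure to reproduce. The check is a comparison of sections plus day arithmetic.

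1. **28-day follow-up.** Sections 8.3 and 3.1 require it of everyone; 6.4 requires it of everyone except re-enrollers. In 6.5 the closing sentence directly follows the exception. If it refers to re-enrollers, 6.5 contradicts 6.4. If it refers to everyone who withdraws, it restates the general rule and leaves the exception unclear. The text does not settle which.

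2. **What stands in for the waived visits.** The Discontinuation Visit has no column in Table 4 and no list of procedures elsewhere. Screening in Table 4 includes viral load and AE recording but no antibody sample. Section 6.3 places antibody samples at Day 1 and EOS only.

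3. **Timing.** Let the last IM dose fall on day t and the loading dose on day t + g, with g > 0.
   - The AE window in 8.3, counted from the last IM dose, closes at t + 28.
   - The new Day 1 is at t + g + 28 or later, so after t + 28.
   - The next required antibody sample, on the new Day 1, therefore falls outside the 28-day window. With g = 14 (assumption: one 2-week dose interval has passed), it is at t + 14 + 28 = t + 42 or later.
   - Viral load is required at re-screening and again on the new Day 1. If re-screening is on the loading-dose day and g = 14, the first value is at t + 14.

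4. **Footnote 3.** It does not say whether the first dose is the first ever or the first of the new enrollment. If it restarts, AE recording from re-screening to the new Day 1 is limited to procedure-related events. Table 4 gives Screening a window of 28 days before Day 1, so this stretch is at most 28 days. In the g = 14 example with re-screening on the loading-dose day and the new Day 1 at t + 42, the stretch runs from t + 14 to t + 42. It overlaps the 8.3 window for 28 − 14 = 14 days, during which 8.3 asks for all AEs and footnote 3 for procedure-related ones only.

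5. **No fallback.** Sections 6.4 and 6.5 exempt subjects who are in the process of re-enrolling; 5.3.2 and 6.3 exempt those who have re-enrolled. A subject who intends to return and never does is exempt under the first pair and not under the second.

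6. **EOS day.** Section 6.3 puts the EOS antibody sample for HIV-infected IM subjects at Day 85. Section 5.3.2 directs discontinued subjects of that group to Days 99 and 113, so following it literally misses the sample; 6.5 does not.

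7. **Size.** One subject in 20 is 1/20 = 5% of the IM Group. The documents do not give the number of re-enrollers; an assumed 1 to 4 would be 5% to 20%.

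**The case against.** The best reply is that little is actually lost. Section 8.3 still obliges the investigator to report AEs, Section 8.2 elicits them at every visit, and two visits are mandatory before re-enrollment. Viral load is drawn at re-screening and the new Day 1, and an antibody sample is drawn on the new Day 1. Subjects re-enroll because of scheduling problems outside the study, and those with a dose-limiting toxicity leave under a separate rule. All of this stands, and it rules out several readings that a reader might infer:

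- *The weeks after stopping IM contain no AE, viral load or antibody data.* They do not: what is missing is a scheduled 28-day contact and an antibody sample timed to the end of the first IM course.
- *A subject whose viral load rebounds can leave unmeasured.* Someone who fails re-screening on the limit of 1,000 copies/mL has, by definition, a recorded value.
- *AE recording is restricted for at least 28 days.* This needs footnote 3 to restart, which it does not say, and the screening window makes 28 days the maximum.
- *The gap makes IM look better.* Nothing in the documents shows that re-enrollers are more prone to reactions, rebound or antibodies.

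The reply does not remove the conflict between 6.4 and 8.3/3.1, the empty Discontinuation Visit, or the missing fallback. A reporting duty without a scheduled contact relies on the subject to volunteer events.

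**Conclusion.** The inconsistency is real and should be corrected. Read as written, Section 6.4 drops a scheduled safety contact that 8.3 and 3.1 presuppose, and the waived EOS visit takes the end-of-IM antibody sample with it. The next antibody sample is due more than 28 days after the last IM dose, and at least 42 days after it if 14 days pass before the loading dose. This assumes that the subject received at least one IM dose before stopping and that the window in 8.3 is counted from that last IM dose. The Day 85 versus Day 99/113 mismatch is a separate drafting fault affecting discontinued HIV-infected IM subjects who do not re-enroll. Each re-enroller is about 5% of the group; how many there will be, and which way any bias would run, cannot be determined from the documents.

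The SAP limits what a protocol change alone can achieve. Under addendum item 2b, safety, viral load and antibody data from the first enrollment are not presented for re-enrolled subjects. The SAP takes Day 1 as baseline for HIV-infected subjects, so an antibody response to the first IM course could appear as a baseline finding of the second.

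**What to change.** 1. Reconcile 5.3.2, 6.3, 6.4 and 6.5 with 8.3 and 3.1, so that AE collection to 28 days after the last dose applies to every discontinued IM subject, and reword the last sentence of 6.5 so that it is clear whom it covers.
2. List the Discontinuation Visit procedures as the assessment rows of the Day 85/EOS column of Table 4, including viral load, safety laboratory tests, antibody sample and injection-site assessment, for every HIV-infected IM subject who stops, re-enrolling or not. This also removes the need for a fallback.
3. State that footnote 3 applies only before the first-ever study dose.
4. Make 5.3.2 name the same EOS visit as 6.5.
5. Amend IM SAP addendum item 2b so that first-enrollment safety, viral load and antibody data after IM dosing are presented. Without this, the added samples would be collected and then left out of the analyses.

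The cost is one set of routine samples per re-enroller, at a visit the protocol already requires, and a little more analysis work. The 28 days after the last IM dose end before the new Day 1, so the follow-up does not delay re-enrollment.

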## 6.5 Early Withdrawal Procedures

Subjects who withdraw or are discontinued from the study at any time before EOS (Day 85 (12 weeks) for HIV-infected Core or IM Groups, or Day 99 for Sentinel and HIV-uninfected Core or IM Groups) will be asked to complete all EOS procedures to ensure safety and to collect as much study data as possible, except for discontinued HIV-infected IM subjects that are re-enrolling into the study. These individuals should be followed for 28 days after receiving study drug administration.

## 6.6 Unscheduled Visits

Unscheduled visits are allowed for the following reasons:

- To perform confirmatory laboratory testing for clinically abnormal values; and
- Any time the investigator feels that it is clinically required for safety reasons related to the subject's participation in this trial.

Findings during these unscheduled visits must be reported in the EDC system under the unscheduled visit section.

## 7. Study Assessments

A central laboratory will analyze all blood and urine samples with the exception of the HIV-1 resistance testing, immunogenicity testing, and PK assessments, which will be undertaken by appropriate specialty contract laboratories. Urine samples will be analyzed at the site; if abnormal results are obtained for a subject, a urine sample will be sent to the central laboratory for microscopic evaluation.

The following assessments will be conducted at the times indicated in the Schedules of Events ([Table 1](#), [Table 2](#), [Table 3](#), and [Table 4](#)).

## 7.1 Activities to be Completed

### 7.1.1 Demographic Data, Medical History, and Concomitant Medications

Demographic data, a complete medical history (per subject report), and documentation of prior medications will be collected at Screening; information about recent or concomitant medications will be obtained at each visit.

### 7.1.2 Complete Physical Examination

A complete physical examination will include the following assessments: skin, head, eyes, ears, nose, throat (“HEENT”), chest including breasts and lungs, heart, abdomen, extremities and neurological exam. Height and weight will be measured at Screening and weight only at other times specified.

